9.3 Confidentiality of Data

Any research data containing subject protected health information (PHI) is confidential. KPSC staff will not discuss the protocol or research data with anyone other than KPSC project personnel, or representatives of GSK. All sharing of confidential information shall be in accordance with the confidentiality agreement detailed in the study contract.

Appendix A: Table shells

Table shells are provided in a separate Excel file.

Appendix B: Underlying condition of vaccine indication

Vaccine recipients will be determined to have the following underlying conditions for vaccination if the associated diagnosis codes are present in the medical record six months prior to index vaccination, including the date of index vaccination.

1. Asplenia

Functional - Hemoglobinopathies (primarily sickle cell [SS or SC] disease)

ICD-9 Codes:

Diagnosis	ICD-9 Diagnostic Code
Sickle cell disease unspecified	282.60
HB-SS disease with crisis	282.62
Sickle cell thalassemia without crisis	282.41
Sickle cell/HB-C disease without crisis	282.63
Sickle cell/HB-C disease with crisis	282.64
Other sickle cell disease without crisis	282.68
Other sickle cell disease with crisis	282.69
Sickle cell thalassemia with crisis	282.42

ICD-10 Codes:

Diagnosis	ICD-10 Diagnostic Code
Sickle cell disease without crisis	D57.1
HB-SS disease with crisis, unspecified	D57.00
Sickle cell thalassemia without crisis	D57.40
Sickle cell/HB-C disease without crisis	D57.20
Sickle cell/HB-C disease with crisis, unspecified	D57.219
Other sickle cell disorders without crisis	D57.80

Other sickle cell disease with crisis, unspecified	D57.819
Sickle cell thalassemia with crisis, unspecified	D57.419
Hyposplenism	D73.0

Anatomic Asplenia

ICD-9 Codes:

Diagnosis	ICD-9 Diagnostic Code
Anomalies of spleen congenital	759.0

ICD-10 Codes:

Diagnosis	ICD-10 Diagnostic Code
Asplenia (congenital)	Q89.01
Congenital malformations of spleen	Q89.09
Acquired asplenia	Z90.81

2. Persistent Complement Component Deficiencies

ICD-9 Codes:

Diagnosis	ICD-9 Diagnostic Code
Other specified disorders involving the immune mechanism	279.8

ICD-10 Codes:

Diagnosis	ICD-10 Diagnostic Code
-----------	------------------------

Defects in the complement system	D84.1
----------------------------------	-------

GlaxoSmithKline

STATISTICAL ANALYSIS PLAN

Study Title: Post-licensure observational safety surveillance study of quadrivalent meningococcal ACWY conjugate vaccine MenACWY-CRM (Menveo[®]) in children 2 months through 23 months of age.

Protocol Number: V59_74OB

Phase of Development: Phase IV

IND number: 11278

Sponsor: GlaxoSmithKline
[name]
[name]

Coordinating/Principal Investigator(s): PPD
Department of Research and Evaluation
Kaiser Permanente Southern California
[name]
[name]

Epidemiologist: [name]
Global Epidemiology
GlaxoSmithKline
Amsterdam, The Netherlands
Email: PPD

Plan Prepared by: PPD, MS
Research Manager, Biostatistics
Kaiser Permanente Southern California

Version and Date: Version 2.0: 17 November 2015

Approvals

Approvers, Organization & Role	Approval Status	Date
PPD [REDACTED], MS KPSC Research and Evaluation Research Manager, Biostatistics	Approved	11/17/2015
PPD [REDACTED] KPSC Research and Evaluation Principal Investigator	Approved	11/17/2015
PPD [REDACTED] Department of Epidemiology GlaxoSmithKline Epidemiologist	Approved	11/17/2015

Publication Record

Version	Date	Primary Author	Description
1.0	September 18, 2015	PPD [REDACTED]	1 st Draft for GSK Review
1.1	October 16, 2015	PPD [REDACTED]	2 nd Draft for GSK Review
1.2	October 30, 2015	PPD [REDACTED]	Final draft for GSK Review
1.3	November 6, 2015	PPD [REDACTED] [REDACTED]	Comments on Draft 1.2
1.4	November 11, 2015	PPD [REDACTED]	Final draft for GSK Review
2.0	November 17, 2015	PPD [REDACTED]	Approvals obtained, SAP finalized

Definitions

Concomitant vaccination(s) – any other vaccination(s) administered to a subject on the same date as a MenACWY-CRM vaccination.

Day 0 - For the calculation of study day, Day 0 is the date when the index vaccination is received.

Event – Events are classified on an encounter level and a diagnosis level. For encounters, an inpatient admission, emergency department (ED) visit, or an ED visit resulting in an inpatient admission will each be treated as a single event. For diagnoses, all medical diagnoses made during ED and inpatient visits are considered events, which will be further classified as pre-existing, new, recurrent, or part of an ongoing episode.

Episode – Diagnosis-type medical events that result in multiple encounters during the observation period are considered episodes. Episodes comprise the course of a disease or condition, from initial presentation through resolution, as determined through chart review. An episode will be consolidated as a single event for analysis. For each episode, the first diagnosis date in any care setting will be used for analyses.

First-dose - no prior dose of a quadrivalent meningococcal conjugate vaccine recorded in the full medical history

Index vaccination – The first receipt of MenACWY-CRM at a KPSC facility between July 1, 2014 and June 30, 2017 in a study subject of which the date of administration defines the start of the observation period.

Observation period - For each individual, the observation period is defined as the time from the first dose of MenACWY-CRM vaccination up to 6 months after the last dose of MenACWY-CRM vaccination received between 2-23 months of age, disenrollment, death, or the end of data collection (November 30, 2017), whichever occurs sooner. For each dose, the observation period is defined as the time from the dose of MenACWY-CRM vaccination up to six months following that dose, receipt of a subsequent MenACWY-CRM vaccination, disenrollment, death, or the end of data collection, whichever occurs sooner.

Pre-existing conditions – Diagnoses occurring in any care setting (inpatient, outpatient, or emergency department) prior to the first dose of MenACWY-CRM vaccination will be searched in electronic medical records for evidence of pre-existing medical events. Events with a history of the same diagnosis prior to the first dose of MenACWY-CRM vaccination will be excluded as a pre-existing condition. The medical records prior to the first dose of MenACWY-CRM will be searched for the same diagnosis code.

ABBREVIATIONS

ACIP: Advisory Committee on Immunization Practices

CBER: Center for Biologics Evaluation and Research

CDC: Centers for Disease Control and Prevention
ED: Emergency Department
EMR: Electronic Medical Record
FDA: Food and Drug Administration
GSK: GlaxoSmithKline
HCP: Health Care Providers
HMO: Health Maintenance Organization
ICD-9: International Classification of Diseases, Ninth Revision
ICD-10: International Classification of Diseases, Tenth Revision
KPSC: Kaiser Permanente Southern California
MenACWY- CRM – Meningococcal Quadrivalent CRM-197 Conjugate Vaccine, Menveo
PHI: Protected Health Information
SAP: Statistical Analysis Plan
SAS: Statistical Analysis System, an integrated system of software published by SAS Institute Inc. for accessing, managing, analyzing, and reporting data

Contents

ABBREVIATIONS	3
1. INTRODUCTION	7
2. STUDY OBJECTIVES	7
3. STUDY DESIGN	7
3.1 Overview of study design.....	7
3.2 Sample Size and Power Considerations	8
3.3 Study population, exposures and outcomes	9
3.3.1 Study population.....	9
3.3.2 Exposure.....	9
3.3.3 Outcomes.....	9
4. ANALYSIS OF STUDY POPULATION AND CHARACTERISTICS	10
4.1 Description of study population selection	10
4.2 Characteristics of MenACWY-CRM recipients	10
5. ANALYSES OF OBJECTIVE	11
5.1 Identification and review of events	11
5.2 Frequency and rate of events	12
5.3 Description of events	12

Appendix B: Underlying condition of vaccine indication15

1. INTRODUCTION

Meningococcal disease remains a significant public health burden, particularly in toddlers and infants. GlaxoSmithKline (GSK)'s quadrivalent meningococcal CRM-197 conjugate vaccine (MenACWY-CRM, or Menveo) is expected to fill this unmet need, and as a first step in the process of licensure across all age groups, MenACWY-CRM was submitted for review by the Center for Biologics Evaluation and Research (CBER) in late 2008, and granted approval for use in individuals aged 11-55 years by the Food and Drug Administration (FDA) on February 19, 2010. As of August 2013 MenACWY-CRM was approved for use in persons 2 months through 55 years of age in the United States. In infants initiating vaccination at 2 months of age, MenACWY-CRM is to be administered as a four-dose series at 2, 4, 6, and 12 months of age. Among children 7-23 months of age who have not previously received a dose of MenACWY-CRM, MenACWY-CRM is to be administered as a two-dose series with the second dose administered in the second year of life and at least three months after the first dose. The Centers for Disease Control and Prevention's (CDC) Advisory Committee on Immunization Practices (ACIP) recommends the meningococcal conjugate vaccine MenACWY-CRM for use in infants and toddlers 2-23 months of age who are at increased risk for meningococcal disease. This study will provide additional information to the current safety knowledge of MenACWY-CRM in the population 2-23 months of age.

This Statistical Analysis Plan (SAP) document provides a detailed description of the data considerations, statistical methods, data analysis and results presentation as previously proposed in its related protocol and amendments, where applicable.

2. STUDY OBJECTIVES

To describe medical events that require emergency department (ED) visit or hospitalization in 6 months following routine MenACWY-CRM vaccination in children 2-23 months of age in a health maintenance organization (HMO) in the United States.

3. STUDY DESIGN

3.1 Overview of study design

This study is a descriptive observational study expected to span multiple years. This study will include members of Kaiser Permanente Southern California (KPSC) HMO vaccinated with MenACWY-CRM as part of their routine clinical care. Patients will be between the ages of 2 and 23 months.

The vaccination period spans three years, with the number of study subjects determined by the number of KPSC members aged 2-23 months who receive their index MenACWY-CRM vaccination between July 1, 2014 and June 30, 2017. The observation period for each recipient is defined as the time from the first dose of MenACWY-CRM vaccination up to 6 months after the last dose of MenACWY-CRM vaccination received between 2-23 months of age, disenrollment, death, or the end of data collection (November 30, 2017), whichever occurs sooner. Vaccination status is obtained from the information in the vaccination records of the electronic medical record (EMR).

Medical events in ED and inpatient care units in children 2-23 months of age who were vaccinated with any dose of MenACWY-CRM vaccine will be described. Medical events that occur up to six months following a dose of MenACWY-CRM, receipt of a subsequent MenACWY-CRM vaccination, disenrollment, death, or the end of data collection, whichever occurs sooner will be captured. Events will be identified from EMRs of ED and inpatient care encounters. Events with a history of the same diagnosis prior to the first dose of MenACWY-CRM vaccination will be excluded as a pre-existing condition. Medical records of these events will be reviewed and described.

All events occurring during the observation period are assessed retrospectively. One subject can experience multiple different events. All identified events will be reviewed by a general physician (study co-investigator) to determine the final diagnosis/diagnoses for the encounter.

3.2 Sample Size and Power Considerations

As the study is descriptive in nature, there is no hypothesis testing and therefore no requirement for a given sample size or power. The sample size will be determined by the total number of children aged 2-23 months vaccinated in KPSC during a three-year period.

Approximately 245,000 infants and toddlers aged 2-23 months were enrolled in the KPSC health plan in the period from 2011 to 2013. Among this population, there were around 60 children aged 2-23 months old with high risk medical conditions. It is estimated that the number of infants with high risk conditions would likely fall between 60-100 in the study period.

The following table provides the width of the confidence intervals for the incidence rate estimates for different sample sizes and observed event rates. It assumes that each individual recipient will provide, on average, one person-year of follow-up among all doses.

Table: Expected confidence intervals by event rate and study sample size.

Event rate per 100 person-years	Number of vaccinated subjects		
	N=50	N=100	N=150
0.1	0.0-7.6	0.0-3.9	0.0-2.7
1.0	0.0-9.4	0.0-5.6	0.1-4.3
10	3.3-23.3	4.8-18.4	5.6-16.5
100	74.2-131.8	81.4-121.6	84.6-117.3

3.3 Study population, exposures and outcomes

3.3.1 Study population

This study will include members of KPSC vaccinated with MenACWY-CRM as part of their routine clinical care, between the ages of 2 and 23 months. Baseline medical history and vaccination status is obtained from the medical records.

3.3.2 Exposure

MenACWY-CRM vaccination will be received as part of routine clinical care. All vaccinations are documented in the EMR at time of administration. This study is strictly observational. MenACWY-CRM will be the only meningococcal vaccine used in children 2-23 months of age to prevent *N. meningitidis* serogroup A, C, W135 and Y caused meningococcal disease in KPSC. While other meningococcal vaccines are available for vaccination of KPSC members over 23 months of age, each vaccine has a unique identifier in the KPSC electronic databases and is therefore distinguishable.

In infants initiating vaccination at 2 months of age, MenACWY-CRM is to be administered as a four-dose series at 2, 4, 6, and 12 months of age. Among children 7-23 months of age who have not previously received a dose of MenACWY-CRM, MenACWY-CRM is to be administered as a two-dose series with the second dose administered in the second year of life and at least three months after the first dose. While health care providers (HCP) are advised to follow the ACIP Recommended Childhood Vaccine schedule, vaccination decisions will be determined by the treating HCP and the caregivers.

3.3.3 Outcomes

Outcomes include medical events that require ED visits or hospitalizations in children 2-23 months of age following any dose of MenACWY-CRM vaccination. Medical events occurring in ED and inpatient settings within 6 months following a MenACWY-CRM vaccination will be searched in the EMR. Evidence of the same pre-existing medical event (based on ICD diagnosis code) will be searched for in all care settings (inpatient, outpatient, or ED) prior to the first dose of MenACWY-CRM vaccination.

Events with a history of the same diagnosis prior to the first dose of MenACWY-CRM vaccination will be excluded as a pre-existing condition. The medical records prior to the first dose of MenACWY-CRM will be searched for the same diagnosis code. As there will be a transition from International Classification of Diseases, Ninth Revision (ICD-9) to Tenth Revision (ICD-10) coding, in the event that the diagnosis following a MenACWY-CRM vaccination is coded using ICD-10, both the same ICD-10 code and an equivalent ICD-9 diagnosis code will be searched in the period prior to the first dose.

If a study subject is first seen in the ED and subsequently transferred to the hospital, this will be treated as a single event.

For each identified ED or inpatient visit the following information will be collected:

- Diagnosis of medical events
- Date of diagnosis: the date of the documented code after any dose of MenACWY-CRM vaccination is considered the date of diagnosis. The date of diagnosis is expressed as the number of days following the 1st, 2nd, 3rd, or 4th dose of MenACWY-CRM vaccination.
- Health care setting: hospitalization or ED or both
- First occurrence vs. recurrence of the diagnosis

One subject can experience multiple different events. In the specific situation where an eligible child received multiple doses during the observation period and the event occurred after the administration of a later dose, the timing of the event is calculated from the date of administration of the most recent dose. In the case of a recurrence of the same condition, the initial diagnosis and the recurrent diagnosis will each be separately described relative to the most recent dose.

4. ANALYSIS OF STUDY POPULATION AND CHARACTERISTICS

All analyses will be performed using SAS Enterprise Guide (version 5.1 or higher).

4.1 Description of study population selection

The selection of the study population will be summarized, including the total number of enrolled members aged 2-23 months and the number of members aged 2-23 months vaccinated with MenACWY-CRM. See Appendix A, Table Shell 1, for details.

4.2 Characteristics of MenACWY-CRM recipients

Characteristics of the study population of infant recipients of the MenACWY-CRM vaccine will be described. The description includes demographics (age, gender), underlying condition of the vaccine indication, if available (see Appendix B), and concomitant and prior vaccinations (any and by type).

Separately, duration of follow-up and number and timing of subsequent MenACWY-CRM vaccinations will be described. Other vaccines received during follow-up will be described by name and whether they were given concomitantly with a subsequent MenACWY-CRM dose.

Descriptive statistics (mean, standard deviation, median, Q1, Q3, minimum and maximum) are presented for continuous variables and frequency distributions (n, %) for categorical variables. See Appendix A, Table Shells 2 and 3, for details. For these tables, information on any cell with count >0 but less than 3 will be suppressed in the final report.

These data will be provided for the entire population and for the following strata if sufficient numbers are available (each reported stratum will have $n \geq 5$ recipients):

- Number of MenACWY-CRM doses received during the study period.

In addition, the frequency of vaccinations will be presented graphically in calendar time intervals, overall and by number of doses as stacked bars to distinguish first, second, third and fourth doses received during the period.

5. ANALYSES OF OBJECTIVE

The outcome data will be provided for the entire population and for the following stratum if sufficient numbers are available ($n \geq 5$ in each stratum):

- Number of MenACWY-CRM doses received during the study period.

5.1 Identification and review of events

Medical events occurring in ED and inpatient settings within 6 months following a MenACWY-CRM vaccination will be searched in the EMR.

Medical events will be characterized two ways: by encounter (hospitalization only, ED only, or both ED and hospitalization) and by diagnosis (see Appendix A, Table Shell 4 for details). The analysis allows for any recurrent events (i.e. different episodes of the same diagnosis) to be counted independently.

For characterization by encounter (Table 4a), all dates used for analysis will be the date of the ED encounter or hospital admission. Encounters will be considered pre-existing if all diagnoses made during the encounter are present in the medical record prior to the first dose of vaccine. Upon chart review by the study physician co-investigator, an encounter will be refuted if it is found to not be a true ED or hospital encounter. Each encounter will be reported as a single event, regardless of the number of diagnoses made during the encounter.

For characterization by diagnosis (Table 4b), all dates used for analysis will be the first date that the diagnosis is recorded in the EMR in any medical setting. A diagnosis will be excluded as pre-existing if the same ICD diagnosis code appears in any medical setting prior to the first dose of MenACWY-CRM vaccination. A diagnosis will be considered refuted if, upon chart review by the study physician co-investigator, there is no evidence of the diagnosis in the medical record. Multiple diagnoses associated with the same episode will be identified, but only the first diagnosis date (in any setting) will be counted in the analysis of each episode. Subsequent diagnoses for the same episode will be marked in Table 4b as “Diagnosis is continuation of an ongoing episode.” An episode will be considered as ended when there is symptom resolution as determined by chart review (e.g., symptoms stated to have resolved or the diagnosis/symptoms have been absent from the medical record before they are mentioned again). In the case of recurrent events, the date used will be the date of the first diagnosis in the medical record following resolution of the prior episode. Recurrent events will be marked in Table 4b as “Diagnosis is a recurrence”. Each diagnosis will be described independently. It is possible that different diagnoses from the same inpatient or ED encounter could have different diagnosis

dates, and that some could be pre-existing while others are in the post-vaccine observation period.

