9.7.3 Statistical Methods

This descriptive study will analyze collected data to report frequencies of MenACWY-CRM exposure and analysis of medical events. The frequencies will be presented as absolute numbers and percentages of relevant total.

Frequency of exposure to MenACWY-CRM vaccination

This descriptive study will report the frequency of exposure among infants and toddlers 2-23 months of age vaccinated at least one dose of MenACWY-CRM during the study period. Frequency of exposure will be summarized as follows:

- Overall
- 1 dose
- 2 doses
- 3 doses
- 4 doses

Analysis of medical events

Eligible medical events in the study will be described as follows:

- Frequency of individual medical events

The frequency of medical events is defined as the total number of each individual event. The frequency will be described by absolute number of each individual medical event and percentage of each individual medical event of total number of captured medical events during the observation period.

If the number of medical events allows, captured medical events will be stratified by dose.

- Rate of medical events

The rate of medical events is defined as the number of all captured events divided by the total person-time following MenACWY-CRM doses administered during the study period. 95% confidence interval of the rate of medical events will be calculated. Person-time for each dose will begin at the vaccination and end at 6 months following vaccination, disenrollment, death, the end of data collection, or receipt of an additional dose of MenACWY-CRM, whichever comes first. If data permit, rate will be further stratified by dose.

▫ Description of medical events

Medical events following MenACWY-CRM exposure in children 2-23 months of age will be described. Medical events will be reviewed and described, at least including age at vaccination, gender, vaccination history, diagnoses, and if available, underlying condition. Recurrence of the same medical event after repeated MenACWY-CRM vaccination of the same person will be included in the description as well.

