5.2 Frequency and rate of events

The frequency of medical events is defined as the total number of each individual event. The frequency will be described by absolute number of each individual medical event and percentage of each individual medical event out of the total number of captured medical events during the observation period and included for analysis (as per Tables 4a or 4b).

The rate of medical events is defined as the number of all captured events divided by the total person-time following MenACWY-CRM doses administered during the study period. The rate and Poisson 95% confidence interval of the rate of medical events will be calculated and presented as number per 1000 person-years using SAS PROC GENMOD.

If the number of medical events allows, captured medical events will be stratified by dose and by the status of the diagnosis as first occurrence or recurrence. Person-time for each dose will begin at the date of vaccination and end at 6 months following vaccination, disenrollment, death, the end of data collection, or receipt of an additional dose of MenACWY-CRM, whichever comes first.

Frequency and rate of events will be characterized two ways: by encounter (hospitalization only, ED only, or both ED and hospitalization) and by diagnosis (see Appendix A, Table Shell 5 for details). For the analysis by encounter, the encounter date will be used to determine the timing of the encounter relative to the timing of vaccine dose. For the analysis by diagnosis, the first diagnosis date for each diagnosis in any care setting will be used to determine the timing of the diagnosis relative to the timing of vaccine dose. The analysis by diagnosis will be stratified by setting of diagnosis and recurrence when the number of events in each stratum is ≥ 5 . The setting of diagnosis reflects whether the diagnosis was captured by automated search in the inpatient setting, ED setting, or both. If possible, diagnoses will be grouped by category, and the frequency and rate of diagnoses will be presented by category.

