5.3 Description of events

Diagnosis-type medical events following MenACWY-CRM exposure in children 2-23 months of age will be described if five or more of a diagnosis or diagnosis grouping are observed. Medical events will be reviewed and summarized, at least including age at vaccination, gender, age at diagnosis, MenACWY-CRM vaccination history, setting of diagnosis, and if available, underlying condition of vaccination. Whether this is a first occurrence or recurrence of the same medical event after repeated MenACWY-CRM vaccination of the same person will be included in the description as well. See Appendix A, Table Shell 6 for details.

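### SAP 5.1 and 5.3 use recurrence in two senses, and no planned output links repeat episodes to doses within a child

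*SAP*

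**What the plan says.** **The promise.** In its account of how events will be described, Protocol 9.7.3 states: "Recurrence of the same medical event after repeated MenACWY-CRM vaccination of the same person will be included in the description as well". SAP v2.0, 5.3 keeps this and refers the reader to Table Shell 6: "Whether this is a first occurrence or recurrence of the same medical event after repeated MenACWY-CRM vaccination of the same person will be included". SAP 3.3.3 adds that, for a recurring condition, "the initial diagnosis and the recurrent diagnosis will each be separately described relative to the most recent dose".

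**The working definition.** SAP 5.1 says: "The analysis allows for any recurrent events (i.e. different episodes of the same diagnosis) to be counted independently". Episodes are separated by clinical course alone: "An episode will be considered as ended when there is symptom resolution as determined by chart review". A recurrence is dated as "the date of the first diagnosis in the medical record following resolution of the prior episode". Dose plays no part in these rules.

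**The outputs.**
- SAP 5.2 says that, numbers permitting, "captured medical events will be stratified by dose and by the status of the diagnosis as first occurrence or recurrence". It does not say whether the two factors are crossed.
- Table Shell 4b has one recurrence count per diagnosis, column (h).
- Table Shell 5b has one block for doses received before the event and a separate block for first occurrence or recurrence.
- Table Shell 6 gives the same two items as separate percentages, for diagnoses or groupings with at least five chart-confirmed episodes.
- SAP 5.2 shows the recurrence strata only where each holds at least five events.
- SAP Section 8 lists six tables and one figure. None is a subject-level listing.

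**The concern.** The protocol and SAP 5.3 ask about a child who has the event, is vaccinated again, and has the event again. SAP 5.1 flags something wider. Two respiratory infections on days 10 and 40 after a single dose receive the same recurrence mark as a seizure on day 1 after dose 1 and again on day 1 after dose 2.

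The study has no comparator and plans no sensitivity analyses (SAP 5.4). Whether an event came back after re-exposure in the same child is therefore one of the more informative things it can report, and the protocol names it specifically. If the report follows the shells, that description is mixed with ordinary repeat illness. In rare diagnoses it may appear only as a bare count in Table 4b.

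**Working it through.** The plan states no figure on this point, so the check asks whether the planned table entries determine the number of recurrences that follow a further dose.

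**1. Three hypothetical data sets.** Each has one diagnosis, 6 children and 8 episodes. Each bracket is a child and lists the dose preceding each episode.

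- A: [1,2] [1,2] [1] [1] [2] [2]
- B: [1,1] [1,1] [2] [2] [2] [2]
- C: [2,2] [2,2] [1] [1] [1] [1]

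| | After dose 1 | After dose 2 | First | Recurrence | Recurrence after a further dose |
|---|---|---|---|---|---|
| A | 4 | 4 | 6 | 2 | 2 |
| B | 4 | 4 | 6 | 2 | 0 |
| C | 4 | 4 | 6 | 2 | 0 |

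Table 6 would show 4/8 = 50% after each dose, 6/8 = 75% first occurrence and 2/8 = 25% recurrence in all three. The last column, which is what the protocol promises, differs.

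**2. Range that fits given margins.** Take doses 1 and 2 only and at most one recurrence per child. Let a, b and c be the children whose two episodes follow doses 1 and 1, 1 and 2, and 2 and 2. With D1 and D2 episodes after each dose and R recurrences, the constraints are a + b + c = R, 2a + b ≤ D1 and b + 2c ≤ D2. The quantity wanted is b.

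| D1 | D2 | R | Possible b |
|---|---|---|---|
| 4 | 4 | 2 | 0 to 2 |
| 6 | 4 | 3 | 0 to 3 |
| 10 | 10 | 5 | 0 to 5 |
| 7 | 1 | 3 | 0 to 1 |
| 5 | 0 | 2 | 0 |

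The third row meets the five-event rule in both recurrence strata (15 first, 5 recurrent) and is still undetermined. The margins settle the answer only in edge cases such as the last row, where every episode follows dose 1.

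**3. Would crossing dose with recurrence be enough?** No. A and C have identical crossed cells (first after dose 1 = 4, first after dose 2 = 2, recurrence after dose 2 = 2) but 2 and 0 recurrences after a further dose. The dose before the earlier episode has to be linked to the dose before the later one within the child.

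**4. Illustration of the mixing.** Assume full adherence, no censoring and a constant event rate. Two unrelated episodes then fall in the same dose window with probability Σw²/(Σw)², where w is the window length in months.
- Doses at 2, 4, 6 and 12 months plus 6 months of follow-up: windows 2, 2, 6, 6. (4 + 4 + 36 + 36)/16² = 80/256 = 31%.
- Two doses 3 months apart: windows 3, 6. (9 + 36)/9² = 45/81 = 56%.
- Two doses 6 or more months apart: windows 6, 6. 72/144 = 50%.
- One dose only: 100%.

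**The case against.** - **The SAP has not dropped the item.** This is right. SAP 3.3.3 and 5.3 both keep it, and SAP Section 7 commits the report to everything the SAP specifies. The gap is a stated commitment with no output assigned to it.
- **SAP 5.3, not 5.1, may govern Table 6.** SAP 5.1 assigns its recurrence mark only to Table 4b, and Shell 6 does not define its column. A reader might conclude that Table 6 measures the wrong thing. The documents do not establish that; they leave the meaning open. The narrower reading does not fit the shell either, because with only two categories a repeat episode within one dose interval has no place.
- **The tables carry some dose information.** Tables 5b and 6 place each episode by doses received. For a diagnosis with two episodes in one child, the Table 5b margins would separate the respiratory from the seizure example, were it not for the five-event rule on the recurrence strata. So a claim that no table could ever show it goes too far.
- **It is not an endpoint.** A reader might treat this as a protocol endpoint or a planned causality assessment. It is one sentence within a descriptive account, in a study with no hypothesis testing (Protocol 9.7.1).
- **Extra columns would often stay hidden.** This stands. SAP 3.2 expects 60 to 100 high-risk children, so few diagnoses may reach five episodes. It is a reason for a listing as well as a column split.

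**Conclusion.** The point holds as an unreconciled definition and a missing output. SAP 5.1 uses recurrence without regard to dose, while Protocol 9.7.3 and SAP 5.3 use it to mean recurrence after a further dose. The planned shells generally cannot show the second. In the worked examples the margins leave the count anywhere from none to all of the recurrences (0 to 2 of 2, 0 to 5 of 5), and they fix it only in edge cases.

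The identifiability result needs no assumption about event rates. The ranges are worked for two doses and at most one recurrence per child. The 31% and 56% are illustrations under the assumptions stated with them. A reader might infer that a third to a half of the recurrences reported here will have no dose between them. The documents do not support that, because the mix of one- to four-dose children, actual adherence and censoring are unknown.

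**What to change.** 1. In SAP 5.1 and 5.3, define two terms: *recurrence after a further MenACWY-CRM dose* (a dose falls between the analysis dates of the preceding and the recurrent episode) and *recurrence with no intervening dose*. State that the first answers Protocol 9.7.3.
2. Split the recurrence columns of Tables 4b, 5b and 6 accordingly. Column (h) is not subtracted in Table 4b's total (i = a-b-e-f-g), so no total changes.
3. Add to SAP Section 8 a de-identified per-child output. For each recurrence after a further dose, it should give the diagnosis, and the dose number and days since the most recent dose for both the earlier and the recurrent episode. This also delivers the SAP 3.3.3 commitment.
4. State that this output is exempt from the five-episode and five-event thresholds of Tables 5b and 6, and say how privacy will be protected. The suppression of counts below 3 in SAP 4.2 is written for Tables 2 and 3 only.

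The split alone is not enough. On the illustrative figures, 69% (four-dose) or 44% (two doses 3 months apart) of chance repeats would still fall after a further dose, so the intervals in item 3 are what make the description useful.

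The cost is some SAP wording, a divided column in three shells and one short listing, with small cells to manage. Dose and diagnosis dates are already extracted, so no new data are needed.
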